#### 8.3 STATISTICAL METHODS

Rev.03, 7 January 2016 Confidential Page 28 of 32

**Document:** TDOC-0056124 **Version:** 1.0; CURRENT; Most-Recent; Effective

Status: Effective

CLARVISTA MEDICAL PROTOCOL CVM-00001 Rev.03

The data analyses will be based on the analysis populations described above. No imputation for missing data will be performed. The statistical summaries will be prepared for HMIOL Cohort 1, HMIOL Cohort 2.

#### 8.3.1 OUTCOMES

Each endpoint will be analyzed based on the Implanted-eye Population and PP Population.

#### 9.0 DATA MANAGEMENT

#### 9.1 DATA QUALITY ASSURANCE

All requested information must be entered on the CRF and confirmable through source documentation. If an item is not available or not applicable, this fact should be clearly indicated.

Data will be entered into a computer database developed specifically for this trial. During the course of the trial, data queries will be generated for data points that are potentially erroneous and require appropriate clarification or correction.

#### 9.1.1 DATA MONITORING

Periodic monitoring (either remote and/or on-site) will take place to ensure data integrity. Study monitoring involves the following elements:

ClarVista personnel, or designee, may meet with investigators prior to the initiation of the study in order to review the adequacy of the subject population, facilities, and equipment with respect to the needs of the study, and to familiarize the investigator and support staff with the study protocol.

ClarVista personnel, or designee, may meet with the investigators at the time enrollment is initiated in order to ensure that subjects are being properly selected, that the methods described in the study protocol are thoroughly understood by the investigator, and that study data are being correctly recorded.

ClarVista personnel, or designee, may visit the clinical site at any time during the course of the study to review and/or collect completed case report forms. Additionally, telephone consultation will occur as necessary during the course of the study to ensure the proper progress and documentation of the study findings.

The study data will be carefully protected, and masking utilized to the extent possible, in order to prevent bias.

#### 9.2 RECORD RETENTION

The investigator shall maintain all subject records for whichever of the following periods is shorter:

- A period of two years after the date on which FDA approves the marketing of the device
- A period of five years after the date on which the results of the study are submitted to the FDA in support of the marketing of the device

The Investigator / Site must contact ClarVista as provided in the Protocol Contacts page prior to discarding or disposing of any study related supplies or documents. The Sponsor retains the right to have all study documents shipped (at Sponsor's expense) for archival purposes, as an alternative to disposal.

Rev.03, 7 January 2016 Confidential Page 29 of 32

Version: 1.0; CURRENT; Most-Recent; Effective

Status: Effective

**Document:** TDOC-0056124

CLARVISTA MEDICAL

PROTOCOL CVM-00001 REV.03

Effective Date: 24-Jun-2019

Page 30 of 32

| Procedure/Assessments   | Day -90
to -0 | Day 0      | 1 Day Visit
(Day 1-2) | 1 Wk Visit (Day
7-14) | 1 Mo Visit (Day
30 - 60) | Window
(Day 1 - 30) |
| Informed Consent        | Х                |            |                          | Χ                        |                             |                        |
| Demographics            | Χ                |            |                          |                          |                             |                        |
| Med/Ophthalmic History  | X                | Χ          |                          |                          |                             |                        |
| Eligibility             | Χ                | X          |                          |                          |                             |                        |
| UCDVA                   |                  |            | X                        | X                        | X                           |                        |
| Manifest Refraction     | Χ                |            |                          | X                        | X                           |                        |
| BCDVA                   | Χ                |            |                          | X                        | X                           |                        |
| Keratometry             | Χ                |            |                          |                          | X                           |                        |
| IOL Power Calculation   | X                |            |                          |                          |                             |                        |
| Slit Lamp Examination   | Χ                |            | X                        | X                        | X                           |                        |
| IOP                     | X                |            | X                        | X                        | X                           |                        |
| Pupil Size              | Χ                |            |                          |                          |                             |                        |
| Dilated Fundus Exam     | Χ                |            |                          |                          | X                           |                        |
| Primary Surgery (HMIOL) |                  | X          |                          |                          |                             |                        |
| Surgeon Questionnaire   |                  | Χ          |                          |                          |                             |                        |
| Optic Exchange          |                  |            |                          |                          |                             |                        |
| (see Table 2)           |                  |            |                          |                          |                             |                        |

# APPENDIX A - TABLE 2: SCHEDULE OF ASSESSMENTS - COHORT 2

| Table 2                  | Cohort 2 - Optic Exchange Complete           |                                |                                |                                 |  |  |  |
|--------------------------|----------------------------------------------|--------------------------------|--------------------------------|---------------------------------|--|--|--|
|                          | Op-Visit 2                                   | Form 1.1                       | Form 2.1                       | Form 3.1                        |  |  |  |
| Procedure/Assessments    | Optic
Exchange Visit
(
+1-301 Days) | OE 1 Day
Visit
(Day 1-2) | OE 1 Wk
Visit
(Day 7-14) | OE 1 Mo
Visit
(Day 30-60) |  |  |  |
| Eligibility              | X                                            |                                |                                |                                 |  |  |  |
| UCDVA                    |                                              | Χ                              | Χ                              | Χ                               |  |  |  |
| IOL Power Calculation    | Х                                            |                                |                                |                                 |  |  |  |
| Keratometry              |                                              |                                |                                | Χ                               |  |  |  |
| Manifest Refraction      |                                              |                                | Χ                              | Χ                               |  |  |  |
| BCDVA                    |                                              |                                | X                              | X                               |  |  |  |
| Slit Lamp Examination    |                                              | Χ                              | Χ                              | Χ                               |  |  |  |
| IOP                      |                                              | X                              | Χ                              | X                               |  |  |  |
| Dilated Fundus Exam      |                                              |                                |                                | Х                               |  |  |  |
| Optic Exchange Procedure | Х                                            |                                |                                |                                 |  |  |  |
| Surgeon Questionnaire    | Х                                            |                                |                                |                                 |  |  |  |

Rev.03, 7 January 2016

Confidential

Page **31** of **32** 

**Document:** TDOC-0056124 **Version:** 1.0; CURRENT; Most-Recent; Effective

Status: Effective

CLARVISTA MEDICAL PROTOCOL CVM-00001 Rev.03

#### APPENDIX B

#### **Surgeon Questionnaire**

#### **Primary Implantation**

- 1. How would you rate the surgical difficulty of the base implantation?
  - a. Easier than a traditional single piece IOL
  - b. Slightly easier than a traditional single piece IOL
  - c. The same as a traditional single piece IOL
  - d. Slightly more difficult than a traditional single piece IOL
  - e. More difficult than a traditional single piece IOL
- 2. How would you rate the surgical difficulty of the optic implantation and assembly?
  - a. Very easy
  - b. Easy
  - c. Neutral
  - d. Difficult
  - e. Very difficult

#### Optic exchange

- 1. How would you rate the surgical difficulty of the optic disassembly?
  - a. Very easy
  - b. Easy
  - c. Neutral
  - d. Difficult
  - e. Very difficult
- 2. How would you rate the surgical difficulty of the optic explantation?
  - a. Very easy
  - b. Easy
  - c. Neutral
  - d. Difficult
  - e. Very difficult
- 3. How would you rate the surgical difficulty of the optic implantation and assembly?
  - a. Very easy
  - b. Easy
  - c. Neutral
  - d. Difficult
  - e. Very difficult

Rev.03, 7 January 2016

Confidential

Page 32 of 32

1 TITLE PAGE

Protocol Number: ClarVista CVM-00001

Medical Specialty: Surgical

Project Name /Number: NA

Sponsor Name & Address: CLARVISTA MEDICAL, INCORPORATED

[name]

[name] [contact] [contact]

Test Article(s) / Product(s): ClarVista HARMONI® Modular Intraocular Lens

System

Document: TDOC-0056125 **Version:** 1.0; CURRENT; Most-Recent; Effective

Status: Effective

Protocol CVM-00001 Statistical Analysis Plan

ClarVista Medical, Inc.

Effective Date: 24-Jun-2019

Statistical Analysis Plan for Protocol CVM-00001

EVALUATION OF VISUAL AND REFRACTIVE OUTCOMES OF THE CLARVISTA HARMONI™ MODULAR INTRAOCULAR LENS SYSTEM

Sponsor ClarVista Medical, Incorporated

[name]

[name] [contact] [contact]

Original Version Date 1 March 2018

Rev.02, 1 March 2018 Confidential Page 1 of 8

Document: TDOC-0056125 **Version:** 1.0; CURRENT; Most-Recent; Effective

Status: Effective

Protocol CVM-00001 Statistical Analysis Plan

ClarVista Medical, Inc.

Effective Date: 24-Jun-2019

Table of Contents

1.	Purpose	. 3
2.	Scope	. 3
3.	Software	. 3
4.	Design and Objectives	. 3
5.	Statistical Analyses	. 4
6.	Sample Size	. 5
7.	Analysis Populations	. 5
8.	Sensitivity Analyses	. 5
9.	Subgroup Analyses	. 5
10.	Interim Analyses	. 5
11.	Deviations from the Statistical Analysis Plan	. 5
12.	References	. 5
Арр	endix A – Assessment Schedule	. 6
Арр	endix B - Surgeon Questionnaire	. 7

Document: TDOC-0056125 **Version:** 1.0; CURRENT; Most-Recent; Effective

Status: Effective

Protocol CVM-00001 Statistical Analysis Plan

ClarVista Medical, Inc.

1. Purpose

This Statistical Analysis Plan documents and describes the planned analyses for the CVM-00001 study. This is a study to evaluate surgeon experience and visual and refractive outcomes of the ClarVista HARMONI™ Modular Intraocular Lens System in primary implantation and optic exchange procedure.

2. Scope

This document is based on the Investigational Plan CVM-00001, Rev.03. Changes to the Investigational Plan may require updates to this document. Analyses described here expand on and supersede those described in the Investigational Plan.

3. Software

Statistical analyses will be performed with SAS System Software version 9.4 or above (SAS Institute, Cary, N.C.), R version 3.3 or above (R Core Team, http://www.R-project.org), or other validated statistical software package.

4. Design and Objectives

The CVM-00001 study is designed as a prospective, multi-center, cohort study. Any pre-planned formal hypothesis tests for this feasibility study are not for the purposes of generating definitive conclusions to support regulatory approval.

The study was carried out at five investigational centers, in the Philippines (3 centers), Panama (1) and Mexico (1).

The study comprises patients with planned removal of cataracts (cortical, nuclear, subcapsular, or a combination) by manual phacoemulsification. The investigator will determine if the test lens is to be implanted in OD, OS, or OU based on target refraction and the best interests of the subject.

All patients will have visits scheduled for 1 Day, 1 Week, and 1 Month following primary cataract extraction. During follow up the Investigator and Subject will decide if an optic exchange in the study eye is in the best interests of the subject based on refractive outcome and target. Subjects with satisfactory outcomes, or those opting not to pursue an optic exchange, will be entered into Cohort 1.

Subjects who opt for an HMIOL optic exchange in their primary eye will be entered into Cohort 2. Optic exchange patients will have visits scheduled for 1 Day, 1 Week, and 1 Month following the optic exchange procedure. These subjects may be followed up beyond 1 month as deemed necessary by the surgeon.

Several cohorts of subjects are specified to help characterize the clinical significance of the study outcomes in eyes with and without optic exchange. These cohorts are defined as follows:

All HMIOL Eyes Cohort: Defined as all study eyes implanted with the study device.

Cohort 1: Defined as the subset of study eyes implanted with the study device without a subsequent optic exchange procedure.

Cohort 2: Defined as the subset of study eyes implanted with the study device with a subsequent optic exchange procedure. Analysis of follow-up visits for this cohort will cover two separate time periods:

- Pre-Optic Exchange, comprising visits following primary cataract extraction, prior to the optic exchange visit (through 1 month).
- Post-Optic Exchange, comprising visits following optic exchange. The baseline for the post-optic
 exchange visits is the last pre-optic exchange visit (1-month).

Separate analyses are planned for each cohort.

Rev.02, 1 March 2018 Confidential Page 3 of 8

Document: TDOC-0056125 **Version:** 1.0; CURRENT; Most-Recent; Effective

Status: Effective

Protocol CVM-00001 Statistical Analysis Plan

ClarVista Medical, Inc.

5. Statistical Analyses

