#### **Endpoints:**

- Uncorrected Distance Visual Acuity (UCDVA)
- Manifest Refraction Spherical Equivalent (MRSE)
- Best Corrected Distance Visual Acuity (BCDVA)
- Surgeon questionnaire
- Secondary Surgical Intervention (SSI) (other than optic exchange)
- Adverse Events (AEs)

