Sulcus placement of a "piggyback" IOL is a procedure that has not been evaluated for safety and effectiveness by the FDA so the use of approved IOLs for this purpose in the U.S. is off-label. Among the complications reported with this procedure are secondary pigment dispersion, iris/pupil irregularities, chronic iritis, hyphema, glaucoma, zonular disruption and/or posterior capsular rupture. Thus, it would be desirable to be able to correct or modify the optical result without the need to implant a "piggyback" IOL with its inherent serious risks.

Rev.03, 7 January 2016 Confidential Page 12 of 32

**Document:** TDOC-0056124 **Version:** 1.0; CURRENT; Most-Recent; Effective

Status: Effective

CLARVISTA MEDICAL PROTOCOL CVM-00001 REV.03

IOL Exchange/Manipulation in general, is technically challenging for the surgeon and poses an iatrogenic risk to intraocular structures including the lens capsule, iris, and endothelium of the cornea. Manipulation of the capsular bag to remove an IOL is the major risk in this setting and can damage the capsular bag including posterior capsular rupture and capsular bag dislocation. The capsular bag cannot be repaired once damaged. This risk increases over time as the capsular bag adheres to the IOL and haptics. Even when IOL exchange is not required, manipulation of traditional IOL's to rotate or center the optic introduces the risk of capsular or zonular damage which can cause further lens instability and lens malposition. Thus, it would be desirable to be able to correct RRE without the need to remove the entire IOL particularly after capsular contraction or fibrosis.

The modular IOL concept will serve as a valuable addition to the armamentarium of cataract surgeons. The goal of this technology is to improve refractive (spherical and toric) outcomes and avoid the significant risks of secondary procedures currently being performed as standard practice to address RRE in an indirect manner. It is anticipated that this modular lens will provide clinical utility in two basic areas, the first being the focus of this study.

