1. Post-operative correction of residual spherical refractive error – Based on existing performance of conventional cataract surgery, researchers have concluded that refractive outcomes in normal eyes should be within 0.5D for 45% and within 1D for 85% of cataract cases. This theoretical performance goal still falls substantially short of the real-world outcomes seen with corneal refractive surgery and which cataract patients and surgeons increasingly demand. As a consequence, secondary procedures to optimize visual outcomes following cataract surgery can be as high as 16% in some practices, particularly for premium lens patients.

Another common approach associated with residual spherical refractive error is referred to as monovision (which can be achieved with contact lenses, corneal refractive surgery, or IOL selection), a monofocal IOL which targets distance vision is used in the dominant eye and the opposite, the non-dominate eye is targeted for near vision. This approach allows patients to see at both distance and near and is a popular choice for patients wishing to achieve spectacle independence.

While it is commonly used for this purpose, not all patients are able to adapt to monovision.  They may have difficulty with acuity-based tasks and with tasks demanding depth perception. Monovision patients may also experience problems with headaches and troublesome visual symptoms such as glare and halos around point sources of light, particularly under low-light conditions. Typically, within three months of the surgery a patient's acceptance or lack of acceptance of monovision correction will be known. At that point, dissatisfied patients are offered glasses to overcome the refractive disparity between eyes. Of course, this is contrary to the patient's desire to be independent of glasses. Furthermore, spectacle correction is not ideal due to the significant imbalance between the required lens power for each eye creating visual discomfort and intolerance (i.e. asthenopia). Refractive surgery on the cornea (e.g., LASIK or PRK) to reverse the over correction of the non-dominant eye is also an option, but not all monovision patients have a suitable cornea (e.g., too thin) and such surgery introduces additional risk.

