#### 3.2.1 INCLUSION CRITERIA

Rev.03, 7 January 2016 Confidential Page 14 of 32

**Document:** TDOC-0056124 **Version:** 1.0; CURRENT; Most-Recent; Effective

Status: Effective

CLARVISTA MEDICAL PROTOCOL CVM-00001 Rev.03

1. Must be able to understand and provide informed consent themselves or through a representative with a witness present on the IRB or EC approved Informed Consent Form (ICF)

- 2. Must be willing and able to return for scheduled treatment and follow-up examinations for at least month study duration
- 3. Must be at least 22 years of age or older at the time of consent
- 4. Planned removal of cataracts (cortical, nuclear, subcapsular, or a combination) by manual phacoemulsification cataract extraction
- 5. Dilated pupil size ≥ 6 mm in primary study eye

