# 3.2.4 EXCLUSION CRITERIA —POST-PRIMARY CATARACT EXTRACTION (AFFECTING ELIGIBILITY FOR HMIOL OPTIC EXCHANGE)

- 1. Any clinical finding or intraocular complication during primary cataract extraction that (in the judgment of the Investigator) is likely to increase complications with optic exchange procedure or present undue risk to the subject (e.g. unexplained endothelial cell loss, post-primary cataract extraction macular edema, persistent ocular inflammation, etc.)
- 2. Presence of YAG Capsulotomy in the primary (HMIOL) eye

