5.1. General Statistical Methods

For continuous measures, descriptive summary statistics will include the number of observations, mean, standard deviation, median, minimum, maximum, as well as the number of eyes with results not reported. For continuous measures analyzed as changes from earlier visits, the 95% confidence interval for change will also be reported. Continuous measures may also be dichotomized or otherwise split into clinically meaningful categories and additionally analyzed as categorical measures.

For categorical measures, the percentage and number of cases for each condition (e.g., 20/20 or better) will be reported. The number of eyes without results will be omitted from the numerator and denominator of such calculations (i.e., no imputation will be performed).

Any calculated p-values will be based on nominal calculations with no adjustment for multiplicity.

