5.6. Effectiveness Endpoints

Effectiveness endpoints will be summarized in the per-protocol population for each cohort at each study visit for which they are available. See Appendix A for a listing of scheduled assessments by visit.

Rev.02, 1 March 2018 Confidential Page 4 of 8

Document: TDOC-0056125 **Version:** 1.0; CURRENT; Most-Recent; Effective

Status: Effective

Protocol CVM-00001 Statistical Analysis Plan

ClarVista Medical, Inc.

Effective Date: 24-Jun-2019

6. Sample Size

The sample size for this study was not based on any statistical criteria. The sample size was chosen to provide sufficient experience and feedback regarding the ClarVista HARMONI™ Modular Intraocular Lens System at five investigative centers.

7. Analysis Populations

Safety Population: Eyes with attempted study lens (HMIOL) implantation, (successful or aborted after contact with the eye). The intraoperative and postoperative AEs and device deficiencies, slit lamp examination, dilated fundus examination, and IOP will be summarized based on the safety population.

Per-Protocol Population: Eyes with successful HMIOL implantation that do not have major protocol deviations (such as improperly enrolled in the study or lens power calculation errors). The effectiveness endpoints will be summarized based on the per-protocol population.

10. Interim Analyses

There are no plans for formal interim analyses for the purposes of study modification or possible early termination. Any interim analyses will be administrative in nature and results will not be distributed to Investigators or subjects to prevent bias from exposure to accruing study results.

Interim Safety Summary: Safety outcomes will be evaluated when all eyes in Cohort 1 and Cohort 2 have completed the 1 Month Visit following primary cataract extraction and optic exchange, respectively (post-optic exchange for Cohort 2).

Final Safety and Effectiveness outcomes will be evaluated when all study subjects complete the final visit or exit the study.

11. Deviations from the Statistical Analysis Plan

Any deviations from the Statistical Analysis Plan will be noted and described with appropriate statistical and clinical rationale as needed.

12. References

1. ISO 11979-7:2014 Ophthalmic implants — Intraocular lenses — Part 7: Clinical investigations.

Rev.02, 1 March 2018 Confidential Page 5 of 8

Document: TDOC-0056125 **Version:** 1.0; CURRENT; Most-Recent; Effective

Status: Effective

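### UCDVA is summarised without regard to each eye's target refraction: near-target eyes, if enrolled, would make it look worse, and target changes at exchange would bias Cohort 2 in either direction

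*SAP*

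**What the plan says.** **Choice of eye and target.** SAP section 4 and the protocol synopsis leave it to the investigator to decide "if the test lens is to be implanted in OD, OS, or OU based on target refraction". Exchange is likewise decided on the refractive result and the target. Nothing requires the target at exchange to be the one set at the primary surgery.

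**Eligibility.** Protocol sections 3.2.1 to 3.2.4 do not mention target refraction. The eye-level inclusion criteria are planned cataract removal and "Dilated pupil size ≥ 6 mm in primary study eye". The post-primary exclusions concern complications and "Presence of YAG Capsulotomy in the primary (HMIOL) eye".

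**Near targets.** The protocol's introduction says that the lens is expected to have "clinical utility in two basic areas, the first being the focus of this study". Inside that first area it describes monovision, in which "the non-dominate eye is targeted for near vision", and the reversal of the near correction when patients do not tolerate it.

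**Analysis.** UCDVA is an endpoint for both cohorts (protocol section 7.1). SAP section 5.6 says: "Effectiveness endpoints will be summarized in the per-protocol population for each cohort at each study visit for which they are available". The SAP cohorts (all implanted eyes, Cohort 1, Cohort 2) are defined by implantation and exchange only. Under SAP section 5.1, for categorical measures "the percentage and number of cases for each condition (e.g., 20/20 or better) will be reported", and measures analysed as change get a 95% confidence interval. Under SAP section 4, the baseline for post-exchange visits is the last pre-exchange visit.

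**The concern.** UCDVA measures lens performance only in an eye meant to see at distance without correction. An eye set for near on purpose has poor UCDVA when everything has gone to plan. Nothing in the visible plan keeps such an eye out of the UCDVA tables. The per-protocol filter would not remove it, because its examples are wrongful enrolment and errors in the lens power calculation, and an intended near target is neither. Accountability is by eye, so a bilateral monovision subject would put one distance eye and one near eye in the same table.

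In Cohort 2, an eye whose target is changed at exchange shows a change in UCDVA that reflects the new target and not the correction of a refractive miss. Visual outcomes are in the primary objective and exchange is the device's distinguishing feature, so this affects how the main descriptive results are read.

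**Working it through.** The plan gives no figure to reproduce. The study tests no hypothesis, the sample size has no statistical basis, and neither the share of near-target eyes nor any expected acuity is stated. The check is mixture arithmetic on assumed inputs, shown over a range.

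**1. After implantation.** Let f be the share of near-target eyes and d the amount by which their UCDVA is worse, taken as 0.3 to 0.7 logMAR.

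- Shift in mean = f × d.
- Pooled percentage = (1 − f) × p(distance) + f × p(near).
- Assumed rates: 70% against 5% reaching 20/20, and 95% against 15% reaching 20/40.

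| f | Mean UCDVA worse by (logMAR) | 20/20 rate (70% if f = 0) | 20/40 rate (95% if f = 0) |
|---|---|---|---|
| 5% | 0.015 to 0.035 | 66.75% | 91% |
| 10% | 0.03 to 0.07 | 63.5% | 87% |
| 20% | 0.06 to 0.14 | 57% | 79% |
| 30% | 0.09 to 0.21 | 50.5% | 71% |

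For example, at f = 10% the 20/20 rate is 0.90 × 0.70 + 0.10 × 0.05 = 0.635. With 50% and 2% as the 20/20 rates instead, f = 20% gives 0.80 × 0.50 + 0.20 × 0.02 = 40.4%, against 50%.

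The spread also grows: pooled SD = √(s² + f(1 − f)d²). With s = 0.15, d = 0.5 and f = 10%, this is √(0.0225 + 0.0225) = 0.212.

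**2. Change after exchange.** Let the true gain in error-correction eyes be g = 0.15 logMAR. Let a changed target move UCDVA by d, up or down.

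- Share r going from near to distance: mean gain = (1 − r)g + r·d.
- Share q going from distance to near: mean gain = (1 − q)g − q·d.

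| Share of Cohort 2 | Near to distance, d = 0.3 / 0.5 / 0.7 | Distance to near, d = 0.3 / 0.5 / 0.7 |
|---|---|---|
| 10% | 0.165 / 0.185 / 0.205 | 0.105 / 0.085 / 0.065 |
| 25% | 0.1875 / 0.2375 / 0.2875 | 0.0375 / −0.0125 / −0.0625 |
| 50% | 0.225 / 0.325 / 0.425 | −0.075 / −0.175 / −0.275 |

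In small numbers: with 20 exchanged eyes, of which 4 go from near to distance with d = 0.50, the mean gain is (16 × 0.15 + 4 × 0.50) / 20 = 0.22.

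**3. Other endpoints.** BCDVA is measured with correction, so the target does not enter. MRSE is affected directly: pooling shifts its mean by f × (near target − distance target), and a changed target at exchange moves MRSE by the change in target.

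**4. With f, r and q all zero,** as in a table limited to distance-target eyes with unchanged target, every shift above vanishes.

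**The case against.** The strongest reply is that the harm is hypothetical. No section says that any study eye will be set for near or have its target changed. The monovision text is background, under a heading about correcting residual spherical error. Deciding exchange on the refractive result and the target reads most naturally as correcting a miss. The assessment schedules contain no near-vision test. The introduction says that acceptance of monovision is typically known within three months, while Table 1 of the schedule shows an exchange window of Day 1 to 30. On that window reversals would probably be few. Table 2 prints the exchange timing as +1-301 Days, so the two entries must be reconciled before this argument can be weighed. All of this limits how likely and how large the effect is. It does not put a restriction or a split into the plan.

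Four stronger readings are tempting, and the documents do not support them:

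- *That UCDVA in this study is distorted.* Near-target eyes are permitted and foreseen, but nowhere counted or required.
- *That the exchange gain is overstated.* The bias can run either way.
- *That the SAP commits to a 20/20 rate and a change analysis for UCDVA.* Both are general provisions of section 5.1. The 20/20 category is an example, and splitting continuous measures into categories is optional.
- *That site or cohort comparisons are invalidated.* The visible text plans no site comparison and no test between cohorts.

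Two further objections stand. SAP sections 8 (sensitivity) and 9 (subgroups) are in the contents but not in the supplied text, and a split by target could sit there. The study is also descriptive, and the protocol allows ad hoc analyses, so a split is permitted even though it is not prespecified.

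**Conclusion.** The point holds in conditional form. Eligibility leaves the target open, the protocol places monovision and its reversal within the study's area of focus, and the supplied SAP text summarises UCDVA in per-protocol eyes by cohort and visit whatever the target. If near-target eyes are enrolled, UCDVA after implantation would be understated. If targets are changed at exchange, any reported Cohort 2 change would mix error correction with change of target, in a direction that depends on which change predominates.

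The size rests entirely on the unknown share of such eyes and on the assumed acuities. It is negligible if there are none, and about half a line of mean UCDVA at 10% near-target eyes with d = 0.5. In Cohort 2, a share of 25% changed targets would be enough to raise a 0.15 gain by more than half or to cancel it. The harm is to interpretation, not to an error rate. This is a cheap improvement to the plan and does not call the design into question.

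**What to change.** First confirm that SAP sections 8 and 9 do not already contain a split by target. If they do not, amend SAP section 5.6:

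- Take each eye's intended target from the IOL power calculation at each surgery. The schedules place that calculation at the pre-operative visit and at the exchange visit.
- Report UCDVA (means, any categories and any change) for distance-target eyes, with near-target eyes on a separate line.
- In Cohort 2, show eyes with unchanged target and eyes with changed target separately.
- Split MRSE in the same way, or report MRSE minus target for all eyes. BCDVA can stay pooled.
- If there are no near-target or changed-target eyes, say so in one sentence. No split is then needed.

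The cost is SAP wording and a few extra table lines, with fewer eyes in the headline UCDVA table. Intended target is not listed as a collected data item, and SAP section 4 describes the study as already carried out, so the target may have to be retrieved from source records.
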